MR carries a risk for subjects who are claustrophobia or have pacemakers, metal pieces, aneurysm clips, large colored tattoos, or any other contraindications for MR. Magnetic resonance (MR) is a technique that uses magnetism and radio waves, not x-rays, to take pictures and measure chemicals of various parts of the body. The United States Food and Drug

Administration (FDA) has set guidelines for magnet strength and exposure to radio waves, and we carefully observe those guidelines.

Subjects will be watched closely throughout the MR study. Some people may feel uncomfortable or anxious. If this happens, the subject may ask to stop the study at any time and we will take them out of the MR scanner. On rare occasions, some people might feel dizzy, get an upset stomach, have a metallic taste or feel tingling sensations or muscle twitches. These sensations usually go away quickly but we will ask subjects to tell the research staff if they have them. There are some risks with an MR study for certain people. If subjects have a pacemaker or some metal objects inside their body, they may not be in this study because the strong magnets in the MR scanner might harm them. Another risk is the possibility of metal objects being pulled into the magnet and hitting a subject. To reduce this risk we require that all people involved with the study remove all metal from their clothing and all metal objects from their pockets. We also ask all people involved with the study to walk through a detector designed to detect metal objects. It is important to know that no metal can be brought into the magnet room at any time. Also, once subjects are in the magnet, the door to the room will be closed so that no one from outside accidentally goes near the magnet.

We want subjects to read and answer very carefully the questions on the MR Safety Questionnaire related to their personal safety. We will be sure that subjects have read the MR Safety Questionnaire and tell us any information they think might be important.

2. **Minimizing Risks:** Describe the manner in which the above-mentioned risks will be minimized.

a. For risks associated with [¹¹C]FLB457

The dose of radiation will be submitted for approval to the Yale-New Haven Hospital Radiation Safety Committee (Y-NHH RSC). All scans will be done in the presence of medical supervision and trained nursing staff in an institution specifically designed to support imaging studies. In the event of serious medical complications, the PET scan facilities have immediate access to or consultation with specialized medical units at the Yale-New Haven Hospital. Preparation of radiopharmaceuticals and performance of PET scans will be by radiochemists, physicians, and technologists of the Department of Diagnostic Radiology, Yale University School of Medicine. These professionals are qualified by training and experience in the safe use and handling of radiopharmaceuticals. Subjects will be asked about their previous radiation exposure and those who have had research exposure within the past year will be excluded if their cumulative annual exposure (including the present study) exceeds FDA limits. The information on the previous radiation exposure of study subjects will be notified to the study doctor. No PET studies will be performed on pregnant or potentially pregnant women, as confirmed by pregnancy testing during evaluation and on each scan day before initiation of any scan procedures. If subjects are breastfeeding they will not be able to participate in this research study.

b. For risks associated with oral d-amphetamine administration

Medical side effects: Subjects will be screened for absence of significant medical history and current medical conditions with a complete medical history, physical examination, routine blood tests, urine toxicology and EKG. The study will be canceled on the day of the scan if several of the subject's blood pressure readings are recorded at >90 for diastolic BP or >140 for systolic BP while at rest. Any automated blood pressure results that are abnormal will be repeated manually.

The manual reading will be the official reading.

Inclusion in the study will be limited to individuals who are between the ages of 18-55.

Patients will be excluded if they have any h/o severe medical or neurological illness, any clinically significant brain abnormality, low Hgb, insulin dependent diabetes, more than one risk factor for coronary artery disease, a history of cardiovascular disease, or hypertension.

Patients will be excluded if they have recently donated blood.

Administration of oral d-amphetamine will take place at the PET center with a physician on site.

Constant EKG and frequent BP monitoring will occur until the vital signs are within normal limits. If the systolic BP reaches or exceeds 200 mmHg for more than 5 minutes, an infusion of phentolamine (5 mg IV, over 10 min) will be initiated to control the blood pressure response.

The study physician will be notified if those parameters are reached and he/she will supervise the treatment.

A twelve lead EKG, a code cart and defibrillator are available in the room in case of complications. In case of chest pain, chest tightness or other symptoms suggestive of cardiac ischemia, the experiment will be cancelled and a twelve lead EKG will be immediately obtained to rule out angina (ST segment elevation or depression as compared to the baseline EKG).

Appropriate treatment will be initiated.

Upon discharge, patients will be given the phone numbers of the study physicians from the Division of Translational Imaging and will follow up at least weekly with the study physician, with in-person sessions in each of the first two weeks after amphetamine administration.

Psychiatric/behavioral side effects: Inclusion in the study will be limited to individuals who are between the ages of 18-55. No individuals with psychiatric disorders will be recruited into this protocol, on or off of medications. All subjects will receive a follow up all 30 days after receiving amphetamine to check that they are feeling well and do not still have effects from the amphetamine challenge.

c. For risks associated with placing an intra-arterial catheter

Risks of radial artery cannulation are minimized by having the procedure performed by an experienced physician. Pain is minimized by local anesthesia. Bleeding is prevented by local pressure applied for a minimum of 15 minutes after catheter removal. Subjects will have their hand and finger blood supply examined after arterial cannulation and again following catheter removal. Also, subjects will be asked to abstain from using aspirin, NSAIDs or anticoagulants. Subjects will be provided a 24 hour emergency physician telephone number to call if they encounter pain, discoloration, numbness, tingling, coolness, hematoma, inflammation, or any other unusual symptoms in the wrist or hand, or fever, chills or drainage from the vascular puncture sites, following the procedure. Nurses will provide the subjects an instruction sheet documenting problems to watch for and procedures to follow should such problems occur. Infection is avoided by adequate cleansing of the skin prior to intravascular line insertion.

d. For risks associated with placing an intravenous catheter

The risks of bruising, clotting, and infection will be minimized by having venipuncture performed by trained and experienced personnel under sterile conditions. To avoid injury due to fainting, the antecubital vein catheter will be inserted when the subjects are recumbent. The blood draws during PET scanning sessions will be obtained from the already inserted catheter, to minimize discomfort.

e. For risks associated with the MRI

To minimize risks, each subject will fill out the MRI Safety Questionnaire before the study. Only subjects who fulfill the criteria by this questionnaire will be eligible for the study. In addition,

subjects will remove all metal (watch, hair pins, jewelry). Before entering the MRI room. If the subject has any metallic prostheses/implants they will be excluded from the study. If a subject becomes anxious during the scan they can request that the MRI scan be stopped.

3. Data and Safety Monitoring Plan:

1. Personnel responsible for safety review and its frequency:

The principal investigator in collaboration with [name] will be responsible for monitoring the data, assuring protocol compliance, and conducting the safety reviews at the specified frequency. During the review process, the principal investigator (monitor) will evaluate whether the study should continue unchanged, require modification/amendment, continue or close to enrollment. Either the principal investigator, the HIC, the FDA, or the RDRC, have the authority to stop or suspend the study or require modifications.

2. The risks associated with the current study are deemed moderate for the following reasons:

We view the risks associated with radiation exposure, amphetamine administration, and arterial line placement as moderate.

Although we have assessed the proposed study as one of moderate risk, the potential exists for anticipated and/or unanticipated adverse events, serious or otherwise, to occur since it is not possible to predict with certainty the absolute risk in any given individual or in advance of first-hand experience with the proposed study methods. Therefore, we provide a plan for monitoring the data and safety of the proposed study as follows:

3. Attribution of Adverse Events:

Adverse events will be monitored for each subject participating in the study and attributed to the study procedures / design by the principal investigator, [name], according to the following categories:

- a.) Definite: Adverse event is clearly related to investigational procedures(s)/agent(s).
- b.) Probable: Adverse event is likely related to investigational procedures(s)/agent(s).
- c.) Possible: Adverse event may be related to investigational procedures(s)/agent(s).
- d.) Unlikely: Adverse event is likely not to be related to the investigational procedures(s)/agent(s).
- e.) Unrelated: Adverse event is clearly not related to investigational procedures(s)/agent(s).

4. Plan for Grading Adverse Events:

The following scale will be used in grading the severity of adverse events noted during the study:

- a. Mild adverse event
- b. Moderate adverse event
- c. Severe

5. Plan for Determining Seriousness of Adverse Events:

Serious Adverse Events:

In addition to grading the adverse event, the PI will determine whether the adverse event meets

the criteria for a Serious Adverse Event (SAE). An adverse event is considered serious if it:

1. is life-threatening
2. results in in-patient hospitalization or prolongation of existing hospitalization
3. results in persistent or significant disability or incapacity
4. results in a congenital anomaly or birth defect OR
5. results in death
6. based upon appropriate medical judgment, may jeopardize the subject's health and may require medical or surgical intervention to prevent one of the other outcomes listed in this definition, or
7. adversely affects the risk/benefit ratio of the study

An adverse event may be graded as severe but still not meet the criteria for a Serious Adverse Event. Similarly, an adverse event may be graded as moderate but still meet the criteria for an SAE. It is important for the PI to consider the grade of the event as well as its "seriousness" when determining whether reporting to the HIC is necessary.

6. Plan for reporting serious AND unanticipated AND related adverse events, anticipated adverse events occurring at a greater frequency than expected, and other unanticipated problems involving risks to subjects or others to the HIC.

The investigator will report the following types of adverse events to the HIC or HSC: a) serious AND unanticipated AND possibly, probably or definitely related events; b) anticipated adverse events occurring with a greater frequency than expected; and c) other unanticipated problems involving risks to subjects or others.

These adverse events or unanticipated problems involving risks to subjects or others will be reported to the HIC within 48 hours of it becoming known to the investigator, using the appropriate forms found on the website.

7. Plan for reporting adverse events:

For the current study, the following individuals, funding, and/or regulatory agencies will be notified (choose those that apply):

- All Co-Investigators listed on the protocol
- National Institutes of Health
- Yale New-Haven Hospital Radiation Safety Committee (RSC/RDRC)

The principal investigator, [name], in collaboration with [name] will conduct a review of all adverse events upon completion of every study subject. The principal investigator will evaluate the frequency and severity of the adverse events and determine if modifications to the protocol or consent form are required.

4. Confidentiality & Security of Data:

Required private identifiable information about individuals, such as their medical history, current medications, psychiatric problems, and family history, will be collected by research staff and be used for research purposes and charting after consent is obtained.

Yale PET Center staff will collect required research data through study procedures as outlined in this protocol, and record it in confidential research records and protected computer files.

Identifiable information is kept in locked file drawers and password protected computer files. Results are published as group data without the use of characteristics that would identify individual subjects. We quote information only by number in conference discussions, scientific reports, or publications, in order to maintain anonymity.

Identifiable research data, including recruitment and screening information and code keys, are stored on a secure database located on the internal PET Center Network. The PET network is protected by a Cisco PIX firewall operated by ITS. All research data are backed up nightly to a Dell PV-136T library with 4 IBM Ultrium-TD2 tape drives using the backup software Legato Networker 7.3 from EMC. Human subjects enrolled in the study are assigned a subject-specific random identifier. Subject identifiers and the means to link the subject names and codes with the research data are stored in separate locations within the database. The software of the database limits the ability to connect the random identifier to the actual subject identification information to research team members only. Access to the database is password protected and each research team member is required to have a unique ID and password to gain access to the database. Authorized users employ their netid and authentication is performed using Yale's central authentication server. Users always access research data through the random identifier only.

At the VACHS, we will use coded records and keep signed consent forms in a locked cabinet. Forms that contain the subjects' names and identifying information will be stored in the medical chart in a locked file. Electronic data is stored in a password-protected database at the VACHS. Access to this database is limited to investigators and research staff within the PIs laboratory.

Their MRI report is transferred to the Yale PET Center and kept on their secure servers described above.

Procedures to ensure confidentiality follow the regulations and policies of the Yale University School of Medicine. The security mechanisms specified above in 4d will continue to be in place to protect study data.

Investigators and research staff at Yale University School of Medicine, VACHS, Yale University Human Investigation Committee (HIC), the FDA, and NIH may have access to the protected health information.

In the event of relevant discovery related to events of abuse, identified health risks, or threats to self or others, as related to the health and safety of the public and/or individual study participants, a report will be made to the relevant agencies and authorities to be conducted as outlined and mandated by HIC guidelines, and Federal, State, and Local Statutes.

5. **Potential Benefits:** Identify any benefits that may be reasonably expected to result from the research, either to the subject(s) or to society at large. (*Note: Payment of subjects is not considered a benefit in this context of the risk-benefit assessment.*)

There are no direct benefits from a subject's participation in this study. This research will benefit scientific knowledge by contributing to the understanding of the role of sex differences and dopamine in tobacco smoking addiction. Society may benefit from these insights, as they may have clinical application in the future.

RESEARCH ALTERNATIVES AND ECONOMIC CONSIDERATIONS

1. **Alternatives:** What alternatives are available to the study subjects outside of the research?

The alternative to participation in this study is to decline participation.

2. **Payments for Participation (Economic Considerations):** Describe any payments that will be made to subjects and the conditions for receiving this compensation.

The subjects will be compensated for their time commitment and inconveniences necessary for completing the study. Subjects will have no financial responsibilities for any portion of the study. Compensation will be up to \$50 for each MRI scan, \$350 for each PET scan, and \$50 for each arterial line. In addition, smoker subjects from Aim 3 will be given a \$100 bonus for completing all portions of the study. Subjects who participate in the Probabilistic Reward Task may also be compensated for the amount that they “win” during the task, up to \$50. Subjects may be provided with payment in a form of a pre paid credit card, cash or a check. In addition, subjects will be provided with a light lunch. They will also be reimbursed for parking on study visit days or they will be compensated for reasonable transportation costs. If participation in the PET Scan has already begun, then compensation will be based on involvement in the study, and will be up to the discretion of the PI. In addition, subjects participating in Aim 3 will be paid \$20 for the script development session. Subjects will be paid either by check, and are advised to allow 4-6 weeks for receipt of payment, or they will be given a pre paid credit card, or cash. Subjects may be compensated for parking for research study appointments. They must show their parking ticket to the Research Staff for verification. Parking tickets will be returned to the subject so they are able to exit the parking lots and they will sign a Parking Voucher for the money received.

Cancellations: If a PET scan should get cancelled for a reason outside of the subject's control (i.e. radiotracer synthesis failure) the subject will be paid \$50 minimum, or a higher amount not to exceed the payment for a full scan day. The amount of the payment for cancellation will be based on the subject's length of participation on that scan day prior to the cancellation, and will be up to the discretion of the PI.

3. **Costs for Participation (Economic Considerations):** Clearly describe the subject's costs associated with participation in the research, and the interventions or procedures of the study that will be provided at no cost to subjects.

There is no cost to subjects for any of the research procedures.

4. **In Case of Injury:** This section is required for any research involving more than minimal risk.

- a. Will medical treatment be available if research-related injury occurs?
Yes

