Structural and functional (resting state) magnetic resonance imaging (MRI) scans (3 T) will be collected in each subject to co-register PET and MRI for image analysis. An MRI will be acquired at the Yale University MRI Center. Subjects will be taken through a ferromagnetic metal detector before entering the scan room. MR images provide a matching anatomical atlas for creating individualized region-of-interest templates for each subject. Subjects may be asked to participate in up to two MR sessions (one MR prior to each PET scan date).

PET experiments

PET experiments will be conducted at the Yale University PET Center.

For Aims smokers and nonsmokers will have up to two [^{11}C]FLB457 scans (2/day when feasible). If technical difficulties arise the second PET scan will be rescheduled as soon as possible.

We may ask subjects to refrain from eating 4-6 hours prior to injection and remain fasting until the study is over. Subjects will also be asked to refrain from drinking caffeinated beverages that day. Smokers may also be asked to abstain from smoking cigarettes starting at 10 p.m. the night before their PET scans day. For all women, a urine pregnancy test will be performed at the beginning of the imaging day at the Yale PET Center.

The preparation of the subject may include the placement of up to two venous lines and an arterial line. The purpose of the arterial line is for blood sampling of [^{11}C]FLB-457 to measure arterial concentration. The purpose of the two venous lines is for the [^{11}C]FLB-457 injection and to measure amphetamine or nicotine levels, respectively.

The arterial line may be placed after infiltration of the skin with 1 to 2% lidocaine by an experienced physician. A study physician or nurse will be present in the PET suite while the arterial line is in place.

Partial immobilization of the head will be done using a felt chin strap. PET scans are acquired as subjects rest using the HR+ or HRRT scanner. A transmission scan is obtained immediately before or after each emission scan.

For the emission scans, 10 mCi or less of [^{11}C]FLB457 will be injected intravenously.

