Following the post-amphetamine PET scan, subjects will be assessed (physical, EKG and vital signs) by one of the investigators. Subjects will be discharged when vital signs are within normal limits and when behavioral changes (if any) are found to be not clinically significant by the MD attending to the subject at the PET Center. If subjects experience any adverse events, they will be treated until they become asymptomatic, prior to discharge.

Behavioral response to amphetamine will be measured by self-ratings with a simplified version of the Amphetamine Interview Rating Scale (van Kammen and Murphy, 1975). Four items will be investigated: euphoria ("feel good"), alertness ("feel energetic"), restlessness ("feel like moving") and anxiety ("feel anxious"). Self ratings will be obtained by analog scales at the following times relative to the d-amphetamine administration: -5 minutes, 0, and hourly thereafter until end of the second scan.

Blood sampling

During the [¹¹C]FLB PET scans, samples may be drawn through the arterial line for determination of [¹¹C]FLB arterial concentration. Samples will be drawn through a venous line to measure amphetamine levels. In the first phase of the study (5-10 min), the arterial input functions are measured with an automated blood counting system (PBS-101, Veenstra Instruments, Joure, The Netherlands) using a continuous withdrawal system where the radioactivity in whole blood is measured with a calibrated radioactivity monitor. Subsequently, individual blood samples may be taken at various time points and will be counted in a gamma counter. Additionally, samples are centrifuged to obtain plasma, which will be counted in a gamma counter, and selected samples will be assayed for the presence of the parent radiotracer compound that has not been metabolized. These measurements will be performed by HPLC analysis. In addition, the fraction of plasma radioactivity unbound to protein will also be determined by ultrafiltration. During the second, post-amphetamine [¹¹C]FLB PET scan, up to 15 blood samples will be collected through a venous line for measurement of plasma amphetamine at selected time points following radiotracer administration.

The total blood sampling volume drawn during the PET Day will be up to 295 mL (125 mL per PET scan) for [¹¹C]FLB analysis, plus up to 100 mL for amphetamine analysis.

Discharge

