subjects for this research project.

Tobacco smokers: n = 40

Healthy nonsmokers: n = 40

Age range: 18-55

Gender: Both groups will include an equal proportion of males and females.

Racial/ethnic group: We will recruit from all ethnic groups available.

3. **Inclusion/Exclusion Criteria:** What are the criteria used to determine subject inclusion or exclusion? How will eligibility be determined, and by whom?

The following are the inclusion and exclusion criteria used. Eligibility to participate in screening session will be determined by the research staff under the guidance of [name] and may be screened under HIC# 0808004163 (PI: [name]). Study participation will be determined after the screening session by the study physician and study PI.

General inclusion criteria:

- men and women, aged 18-55 years
- who are able to read and write
- who are able to give voluntary written informed consent
- have no current uncontrolled medical condition such as neurological, cardiovascular, endocrine, renal, liver, or thyroid pathology
- have no history of a neurological or psychiatric disorder, e.g., no DSM-IV Axis 1 diagnosis in 2 preceding years)
- drink less than 21 drinks/week for women and less than 35 drinks per week for men
- do not suffer from claustrophobia or any MRI contradictions
- able to participate in imaging studies including 2 PET scans and 1 MRI scan
- nonsmokers (smoked < 100 cigarettes in lifetime with urinary cotinine levels 0-30 ng/mL both at intake evaluation and on scan day)
- smokers (smoked at least 10 cigarettes/day for at least one year with an FTND \geq 3, urine cotinine >150 ng/mL and CO \geq 12 ppm at intake)

General exclusion criteria:

- psychosis
- presence of acute or unstable medical or neurological illness. Subjects will be excluded from the study if they present with any history of serious medical or neurological illness or if they show signs of a major medical or neurological illness on examination or lab testing including history of seizures, head injury, brain tumor, heart, liver or kidney disease, eating disorder, diabetes.
- regular use of any psychotropic drugs including anxiolytics and antidepressants and other over-the-counter medications and herbal products within the last six months, that in the PI's assessment would put the subject at increased risk or would be detrimental to the study data.
- pregnancy/Breast feeding (as documented by pregnancy testing at screening or at days of the imaging studies),

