The frequent somatic side effects of d-amphetamine administration are cardiovascular (hypertension, palpitations, tachycardia, bradycardia, orthostasis). General effects such as sweating, feeling warm or cold, nausea, diarrhea, muscle and abdominal cramping, have been reported frequently. Behavioral effects in this dose range are increased level of alertness, talkativeness, restlessness, agitation, mood changes (usually euphoria) and anxiety. In our experience, these effects are generally transient and well tolerated. This dose of amphetamine has not been reported to induce psychotic symptoms in non-schizophrenic subjects. Infrequently blurred vision, headaches and chest tightness, and changes in EKG have been reported. There is a rare risk of permanent neurological damage and death as a result of cardiac arrest or stroke.

Psychiatric or behavioral side effects: General behavioral effects of the injection of amphetamine in this dose range are increased level of alertness, talkativeness, restlessness, agitation, mood changes (usually euphoria) and anxiety. In our experience, these effects are generally transient and well tolerated. This dose of amphetamine has not been reported to induce psychotic symptoms in non schizophrenic subjects and we confirm this observation.

c. Risks of placing an intra-arterial catheter

On the PET scan day a radial arterial catheter will be inserted. Arterial sampling may be associated with mild-to-moderate pain or bruising at the puncture site. In rare instances blocking of the artery, poor healing, hematoma, inflammation, or infection at the catheter insertion site may occur. Certain individuals may feel light-headed during arterial catheter placement.

d. Risks of placing an intra-venous catheter

Drawing blood and inserting an intravenous line (IV) into an arm vein are safe and standard medical procedures. Sometimes a bruise will occur at the puncture site and rarely a blood clot or infection will occur in the vein. Certain individuals may feel light-headed during venipuncture. The volume of blood collected during this study, include screening laboratories, will be approximately 19 tablespoons. This is not expected to have any serious negative effects on a study participant.

e. Risks of an MRI scan

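### The PET-day blood limit does not add up: two scans at 125 mL make 250 mL, not 295 mL, and the whole-study volume in Section VI needs reconciling with it

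*Combined protocol and SAP*

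**What the plan says.** The Blood sampling part of section 3 (Research Plan) gives the limit in one sentence: "The total blood sampling volume drawn during the PET Day will be up to 295 mL (125 mL per PET scan") for analysis of the tracer, and then "plus up to 100 mL for amphetamine analysis". The same section describes what the blood is for. For the tracer, "samples may be drawn through the arterial line for determination of" its arterial concentration. For the drug, "up to 15 blood samples will be collected through a venous line for measurement of plasma amphetamine" during the second scan.

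The number of scans in the current design is two. The PET experiments text and the Discharge text both describe two scans, the drug identification and radiation dosimetry text counts two injections, and an inclusion criterion requires that subjects be "able to participate in imaging studies including 2 PET scans and 1 MRI scan".

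Arterial sampling is worded as optional in PET experiments: "The preparation of the subject may include the placement of up to two venous lines and an arterial line", and "The arterial line may be placed after infiltration of the skin". The arterial-catheter paragraph of Section VI, by contrast, describes insertion on the PET day as definite.

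Section VI, 1. Risks, under the intravenous catheter, gives a second volume: "The volume of blood collected during this study, include screening laboratories, will be approximately 19 tablespoons". It adds that no serious ill effect is expected from this.

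**The concern.** The per-scan figure stands in parentheses as the breakdown of the total, and both are for tracer analysis. They should therefore agree, and they do not. Staff working from the per-scan figure would stop at 250 mL, while staff working from the total could go to 295 mL. This is the stated daily limit on blood drawn from healthy volunteers who get no direct benefit, so it should be one number that can be checked.

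The Section VI figure raises a related question. It is meant to cover the whole study, screening laboratories included, yet it is smaller than the tracer ceiling for the PET day taken alone. The reassurance about risk is attached to that smaller volume.

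**Working it through.** **Inputs**

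- Tracer total: up to 295 mL (Blood sampling).
- Tracer volume per scan: 125 mL (Blood sampling).
- Amphetamine samples: up to 100 mL, up to 15 samples (Blood sampling).
- Scans per subject: at most 2 (PET experiments; Discharge; drug identification text).
- Whole-study volume with screening: about 19 tablespoons (Section VI, Risks).
- Millilitres per tablespoon: 14.79 to 15. This is an assumption; the documents give no conversion.

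**Step 1. Try to reproduce 295 mL.** Total = scans × volume per scan.

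| Reading | Sum | Result (mL) |
|---|---|---|
| 1 scan | 125 | 125 |
| 2 scans | 2 × 125 | 250 |
| 3 scans | 3 × 125 | 375 |
| 4 scans | 4 × 125 | 500 |
| 1 scan + amphetamine | 125 + 100 | 225 |
| 2 scans + amphetamine | 250 + 100 | 350 |

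None gives 295. In the other direction, 295 / 125 = 2.36 scans, which is not a whole number, and 295 / 2 = 147.5 mL per scan, which is not the stated 125.

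**Step 2. Size of the gap.** 295 − 250 = 45 mL. 45 / 250 = 18%; 45 / 295 = 15%. That is too large for rounding.

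**Step 3. Where the 45 mL could belong.** If 295 mL was meant to include everything, 295 − 250 = 45 mL would be left for amphetamine, or 45 / 15 = 3 mL for each of 15 samples. The printed 100 mL gives 100 / 15 = 6.7 mL each. The documents state no per-sample volume, so neither can be confirmed. The sentence adds the amphetamine volume on top of 295 mL, which counts against this reading.

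**Step 4. Section VI.** 19 × 14.79 = 281 mL; 19 × 15 = 285 mL. Against the tracer ceiling alone: 295 − 285 = 10 mL and 295 − 281 = 14 mL, before any amphetamine or screening blood. Conversely, 295 / 15 = 19.7 and 295 / 14.79 = 19.9 tablespoons, so 295 mL as an all-inclusive PET-day total would lie close to the Section VI figure, though still without screening blood.

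**Step 5. What stops a firm maximum being computed.** Two further statements bear on the total:

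- The research plan lists hormone plasma samples at five time points and gives no volume. They are tied to a stress challenge, so they may not belong to this aim.
- The radiation-risk paragraph of Section VI speaks of up to four injections, against two elsewhere.

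The sums 250 + 100 = 350 mL and 295 + 100 = 395 mL are therefore only what the Blood sampling figures give under two readings. They are not established maxima.

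**The case against.** The best defence is that 295 mL is a ceiling, and 250 mL does not exceed it, so following the per-scan figure never breaches the total. That is true, and it means no subject is put over a stated limit by the mismatch. It does not explain why a ceiling should be broken down into parts that fall 45 mL short of it.

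A second defence is that the 45 mL is the hormone sampling. The documents give those samples no volume, and the sentence assigns the 295 mL to tracer analysis. If this is the explanation, the sentence is mislabelled and still needs correcting.

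A third is that Section VI gives an approximate, probably expected, volume while Blood sampling gives ceilings. This stands. A reader might infer that Section VI contradicts the procedures or understates the draw by 65 mL or more (350 − 285 = 65). The documents do not support that. Arterial sampling is optional in the procedural text, the actual draws may fall below their ceilings, and the larger shortfalls rest on the 350 or 395 mL sums, which are themselves unconfirmed. That Section VI does not label its figure as expected or maximum is missing detail, not an error.

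**Conclusion.** The sentence is wrong as written. The per-scan figure and the tracer total differ by 45 mL (18% of 250 mL), and nothing in the documents accounts for it. This rests only on two scans per subject, which the current design text supports consistently apart from the four-injection paragraph; four scans would make 500 mL and fit worse. The documents do not show which of 125, 295 or 100 mL is at fault.

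A narrower point also stands. The whole-study figure of 281 to 285 mL, on the assumed tablespoon, is 10 to 14 mL below the tracer ceiling alone, so the two volume statements need to be reconciled.

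A reader might go further and infer that the risk conclusion is unsound or that participants were given a wrong figure. Neither follows. Nothing in the documents shows that a somewhat larger volume would change the risk assessment. Screening includes a blood count, and recent blood donation and low haemoglobin are exclusions. The consent form is not in the text reviewed.

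Severity is low. The endpoint, sample size and analysis are not affected.

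**What to change.** 1. The investigator confirms which of the three figures is wrong: 125 mL per scan, 295 mL in total, or 100 mL for amphetamine. The check should include the possibility that 295 mL was the all-inclusive total with 45 mL for amphetamine.
2. Blood sampling then states one PET-day maximum covering tracer and amphetamine samples and, if they apply to this aim, the hormone samples with their volume.
3. In Section VI, reconcile the four-injection text with the two-scan design first. Then restate the whole-study maximum from the confirmed figures plus screening blood. If 19 tablespoons is an expected volume, it can stay beside the maximum, labelled as such.
4. Insert no replacement tablespoon figure before these inputs are confirmed.

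The cost is a query to the investigator and a few sentences of text. Unless the investigator's answer shows otherwise, procedures and visits stay as they are; sample size and analysis do not change.
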